3.2. Endpoints

Primary Endpoint

The default primary endpoint is clinical status (8-point ordinal scale) on Study Day 8:

1. Not hospitalized, no new or increased limitations on activities;
2. Not hospitalized, but new or increased limitation on activities and/or requiring new or increased home oxygen, CPAP, or BiPAP;
3. Hospitalized, not requiring new or increased supplemental oxygen - no longer requires ongoing medical care;
4. Hospitalized, not requiring new or increased supplemental oxygen - requiring ongoing medical care (COVID-19 related or otherwise);
5. Hospitalized, requiring new or increased supplemental oxygen;
6. Hospitalized, requiring new or increased non-invasive ventilation or high-flow oxygen devices;
7. Hospitalized, on invasive mechanical ventilation or extracorporeal membrane oxygenation (ECMO);
8. Death.

Key Secondary Endpoints

One of the key secondary endpoints is time to sustained recovery (up to and including Study Day 60) and is defined as the first day on which the subject satisfies 1 of the following 3 categories from the clinical status ordinal scale (and does not return to a score of ≥ 4 up to and including Study Day 60):

1. Not hospitalized, no new or increased limitations on activities;
2. Not hospitalized, but new or increased limitation on activities and/or requiring new or increased home oxygen, CPAP, or BiPAP;
3. Hospitalized, not requiring new or increased supplemental oxygen - no longer requires ongoing medical care.

The other key secondary endpoint is whether the subject did not satisfy one of the following two categories from the ordinal scale up to and including Study Day 29. This analysis will only be completed for those subjects with baseline ordinal score of 5 or 6:

7. Hospitalized, on invasive mechanical ventilation or ECMO;
8. Death.

If the key secondary endpoints are different than what is covered in this master SAP, it will be highlighted for each individual investigational intervention in the corresponding stage-specific appendix.

Other Secondary Endpoints

The other secondary endpoints are:

Efficacy

- Time (days) from Study Day 1 to the first day for which a subject is assessed to be at least 1 category lower (improvement) than the subject's baseline ordinal score up to and including Study Day 60;
- Time (days) from Study Day 1 to the first day for which a subject is assessed to be at least 2 categories lower (improvement) than the subject's baseline ordinal score up to and including Study Day 60;

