4.4.3. Method of Assigning Subjects to Treatment Groups (Randomization)

Randomization will be stratified by study site and severity measured by baseline ordinal score (baseline ordinal score of 5 versus a baseline ordinal score of 6 or 7).

Subjects will first be randomized to 1 of the stages to which they are eligible with equal allocation. Then patients are randomized to the active intervention or placebo version of that stage with allocation $k:1$, where k is the number of interventions for which a subject is eligible. For example, if a subject is eligible for 3 active interventions or stages that the site is currently randomizing, the subject will be randomized to 1 stage with a 1:1:1 allocation to the 3 stages, then randomized to the selected intervention's or stage's active or placebo arm with a 3:1 allocation of active versus placebo. This process results in equal allocation of the 3 active intervention arms and the pooled placebo arm.

Differing entry criteria across interventions adds complexity to this process. Subjects who are eligible for all 3 interventions will be randomized to A, B, or C in the first randomization step, and then have a 25% chance of randomization to placebo in the second step. However, the subject who is not eligible for C will first be randomized to stages with A or B with equal probability, and will have a 33% chance of randomization to placebo in the second step, leading to equal size A, B, and pooled placebo groups for this stratum of subjects. Ultimately, evaluation of A versus placebo would need to only include subjects that were eligible to be randomized to A.

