5. SAMPLE SIZE CONSIDERATIONS

We have chosen a sample size of 100 per arm for the proof of concept stages. The power can be computed for the Study Day 8 ordinal score on the basis of an odds ratio representing clinical improvement. The odds ratio represents the odds of improvement in the ordinal scale for treatment relative to placebo. The sample size to detect a given odds ratio for 1:1 randomization using a 2-tailed test at level α is given by

$$\frac{12(z_{\alpha/2} + z_{\beta})^2}{\lambda^2(1 - \sum_{i=1}^K p_i^3)}$$

where λ is the log odds ratio, p_i is the overall probability (combined over both arms) of being in the i^{th} category of the K ordinal outcomes, $z_{\alpha/2}$ and z_{β} are the $1 - \alpha/2$ and $1 - \beta$ quantiles, respectively, of the standard normal distribution.

However, to fully understand all aspects of the testing procedure, we have simulated the probabilities of an intervention: a) being declared futile after 50 subjects per arm, b) being declared efficacious after 50 subjects per arm, and c) being declared promising by 100 subjects per arm.

The interim analysis will find an intervention futile if its point estimate for the primary endpoint has an odds ratio <1 . An intervention can be declared efficacious early after 50 subjects per arm if two-sided $p < 0.001$ and $OR > 1$. If the intervention continues to 100 subjects, it will be declared promising if the final p -value is < 0.20 and $OR > 1$, and statistically significant if the final p -value is < 0.05 . More details are provided in Interim Analysis Section.

Table 4 displays the outcome probabilities in the control arm for sample size determination; this uses preliminary unpublished data from the remdesivir arm in ACTT study. The categories of the 8-point ordinal scale are described in Section 3.2.

Table 4: Expected distribution of ordinal outcomes for the control arm at Study Day 8

Severity Outcome	Outcome (%)
1. Not hospitalized, no new or increased limitations on activities	0.0
2. Not hospitalized, but new or increased limitation on activities and/or requiring new or increased home oxygen, CPAP or BiPAP	34.6
3. Hospitalized, not requiring new or increased supplemental oxygen - no longer requires ongoing medical care	1.2
4. Hospitalized, not requiring new or increased supplemental oxygen - requiring ongoing medical care (COVID-19 related or otherwise)	10.6
5. Hospitalized, requiring new or increased supplemental oxygen	17.1

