6. GENERAL STATISTICAL CONSIDERATIONS

6.1. General Principles

This is a proof of concept double-blind placebo controlled randomized trial testing a superiority hypothesis where interventions with a two-sided p-value $< .20$ will be declared promising and will be considered statistically significant if the final two-sided p-value is $< .05$. These data will be summarized by treatment (intervention name versus placebo) and when appropriate by baseline ordinal score. Additionally, data will be described according to the appropriate summary statistics, e.g.

- Percentages/proportions/odds ratios for categorical data. For tabular summaries of percentages/proportions, the denominator (e.g., number of subjects in the specified population) will be displayed.
- Means, standard deviation, median, and/or range for continuous data, median and confidence intervals for time-to-event data.

Confidence intervals will be generated; 95% and 80% confidence intervals will be generated for primary and key secondary outcomes. For hazard ratio and odds ratio estimates, Wald confidence intervals will be used. For confidence intervals of proportions for other efficacy and safety outcomes, Blaker confidence intervals will be used.

In general, all tables will have corresponding listings of data presented unless noted otherwise.

When calculating treatment effects (e.g., differences, hazard ratios, odds ratios) from regression modelling, placebo will be used as the reference group. Subjects on interventions will only be compared to control subjects who could potentially have been randomized to that intervention (i.e., they met eligibility criteria for the intervention and are at a site where the intervention was enrolling at the time of the subject's randomization). Analyses of newly added arm(s) will be performed comparing concurrently enrolled control subjects. For any modeling that uses covariates defined in Section 6.4, the category listed last for each variable in that section will be used as the control group for the interaction analysis and covariate-adjusted analyses.

For the time-to-event analyses, the following SAS pseudocode will be used to generate stratum-specific median time to event estimates and confidence intervals and stratum-specific Kaplan-Meier curves.

```
proc lifetest data=dataset plots=(s);
  time timevariable * censorvariable(1);
  test treatmentvariable;
run;
```

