In this approach, `timevariable` represents the time until the event in question (e.g., recovery), `censorvariable` represents the censoring variable (e.g., 0= event observed, 1= event did not occur at the time of withdrawal, discharge, lost-to-followup, etc), and `treatmentvariable` represents the intervention (e.g., 0= remdesivir + placebo, 1= remdesivir + new treatment).

To perform a Cox proportional hazards analysis and generate the treatment hazard ratio along with its Wald confidence interval and p-value from the score test after adjusting for other covariates, the following SAS pseudocode will be used.

```
proc phreg data=dataset;
  class treatmentvariable(ref=placebolabel) othercovariates;
  model timevariable * censorvariable(1) = treatmentvariable othercovariates /
  ties=efron;
  hazardratio treatmentvariable / diff=ref cl=wald;
```

```
ods output hazardratios = hrest globaltest=pvalue;
run;
```

To assess the assumption of proportional hazards for Cox models, Kaplan-Meier curves for each treatment arm will be produced (PH assumption supported if curves do not cross). Restricted mean survival time along with its 95% CI will be reported to assess whether the results change if the PH assumption is not satisfied.

Proportional Odds analysis without MI:

The following SAS pseudocode will be used to perform the proportional odds analysis with treatment, baseline ordinal score and baseline steroid use as covariates to generate the treatment odds ratio, p-value, and predicted probabilities of the ordinal scale levels by treatment and ordinal score using complete data

```
proc logistic data=dataset out=imp_parms plots(only)=effect(x= ordscore_d8
  sliceby =baseordscorevar*trtvar individual connect);
  class baseordscorevar (param=ref ref=5) basesteroidusevar (param=ref ref=no
steroid use) trtvar (param=ref ref=placebolabel);
  model ordscore_d8 = trtvar baseordscorevar basesteroidusevar;
  oddsratio trtvar;
  ods output oddsratioswald = orest;
run;
```

For the endpoints analyzed by proportional odds, odds ratios between the binary progression strata will be computed, to support data understanding. For example, odds ratio, confidence intervals from logistic regression will be reported for treatment effect for the binary endpoint of OS= 1-7 vs 8, then OS= 1-6 vs 7-8, etc. Similar odds ratios across these 7 2x2 tables will support the proportional odds assumption.

95% Blaker confidence intervals for proportions/percentages:

```
proc freq;

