6.4.2. Covariates for Secondary Endpoints

The main analysis for time to sustained recovery will use baseline steroid use and actual baseline ordinal score as covariates in a Cox regression model. P-value from the score test of this adjusted Cox model will be used to compare the covariate adjusted time to sustained recovery between treatment arms. This analysis will be referred to as the primary analysis of the time to sustained recovery endpoint. In the supplemental analysis, time to sustained recovery endpoint will be analyzed using baseline steroid use, actual baseline ordinal score, continuous age, and continuous duration of symptoms prior to enrollment as covariates in the Cox model.

Survival without respiratory failure up to and including Study Day 29 will be analyzed only for subjects with an actual baseline ordinal score of 5 or 6. The main analysis for this endpoint will use a logistic regression model adjusted for baseline ordinal score (5 vs 6/7), baseline dexamethasone use (yes or no), continuous

baseline CRP value, and continuous age as covariates. Additionally, the proportion of subjects who are alive and without respiratory failure up to and including Study Day 29 will be presented by treatment along with 95% and 80% CI estimated from Kaplan Meier. As a sensitivity analysis, survival without respiratory failure will be analyzed using a logistic regression model adjusting for baseline steroid use and actual baseline ordinal score as covariates. A supplemental analysis of this endpoint will use a logistic regression model adjusting for baseline steroid use, actual baseline ordinal, continuous age, and continuous duration of symptoms prior to enrollment.

The analysis of the time to mechanical ventilation or death will include baseline ordinal score (5 vs 6/7), baseline dexamethasone use (yes or no), baseline CRP value and age as covariates in the Cox regression model.

A detailed list of covariates and subgroup analyses to be performed for secondary endpoints is also provided in [Table 6](#).

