If a subject's last assessment is before Day 57 and is discharged to a location other than hospice, another hospital, or long-term care facilities, the subject will be considered recovered at the time of discharge for the sensitivity analysis but may be reviewed by the Endpoint Review Committee, if other data suggests the subject may not be recovered (e.g., to a location other than a private residence or discharged on high flow oxygen). If a subject is discharged to hospice or another hospital, or is a special case where recovery handling may be unclear, the subject's data may be reviewed by the Endpoint Review Committee to make the determination of whether the subject should be considered to have sustained recovery and, if so, at what time point in the analyses. Subject data to be reviewed as part of this determination will include the reported clinical status scores while hospitalized, where the subject was discharged to (e.g., private residence, rehabilitation facility, long-term care/nursing home, comfort care), and any information regarding readmittance. Additional information may be solicited to assess recovery.

Refer to [Table 6](#) for a list of covariates and subgroup analyses for this endpoint. Refer to [Table 7](#) for imputation methods to be applied to this endpoint.

The main analysis of the first key secondary endpoint (time to sustained recovery up to and including Study Day 60) conducts a score test to compare treatment to control up to and including Study Day 60. The treatment median survival time, confidence intervals and p-value from the score test will be presented ([Table 28](#)). Restricted mean recovery time estimates will be provided for each treatment group and actual baseline ordinal score stratum as well as the difference in restricted mean recovery time between treatment groups within each of the baseline ordinal score strata ([Table 29](#)).

Kaplan-Meier curves for each treatment arm will be presented and supplemented with the hazard ratio estimate, p-value, and the number of subjects at risk in each treatment at Study Day (not necessarily actual Study Days 1, 3, 5, 8, 11, 15, 22, 29, and 60) ([Figure 8](#)).

If the key secondary endpoint is different than what is covered in this SAP, it will be highlighted for each individual stage in the corresponding stage-specific appendix along with the subsequent analysis.

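### Non-crossing Kaplan-Meier curves do not establish proportional hazards, and the restricted mean times that SAP section 6.1 promises are missing for several Cox endpoints

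*SAP*

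**What the plan says.** SAP section 6.1 sets out the PH check for Cox models in two sentences. The first is "Kaplan-Meier curves for each treatment arm will be produced (PH assumption supported if curves do not cross". The second is "Restricted mean survival time along with its 95% CI will be reported to assess whether the results change if the PH assumption is not satisfied". The SAP gives no residual test, log-log plot or time-by-treatment term, and does not say how large a sign change counts as a crossing.

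The check therefore covers every Cox analysis: sustained recovery (6.4.2, 8.2.1), one- and two-category improvement and ventilation or death (8.2.2), and mortality and the safety composite (9.4). Sustained recovery is the prominent one: "One of the key secondary endpoints is time to sustained recovery (up to and including Study Day 60"). For it, "P-value from the score test of this adjusted Cox model will be used to compare the covariate adjusted time to sustained recovery" between arms.

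RMST is planned without any condition for recovery (section 8.2.1: "Restricted mean recovery time estimates will be provided for each treatment group and actual baseline ordinal score stratum", shown in Table 29) and for death (section 9.4, Table 55). The shells for improvement (Tables 32-33), ventilation or death (Tables 42-43) and the safety composite (Table 56) have no RMST entry.

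**The concern.** Proportional hazards means that the ratio of the two hazards is constant over time. Whether survival curves cross depends on the sign of a cumulative difference, which is a different property. If HR differs from 1 and is constant, the true curves cannot cross, so non-crossing is necessary; it is not sufficient. If HR is 1, the true curves coincide and the sample curves will tend to cross by chance although hazards are exactly proportional.

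The trial is meant to supply estimates for the sample size and endpoint choice of a larger trial (SAP 4.1). A hazard ratio carried forward as PH-supported only because the curves stayed apart could hide a large change in effect over time. Conversely, a chance crossing could cast doubt on a sound analysis. Where no RMST row exists, the reader has nothing else to go on.

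The same section treats proportional odds better. It compares the estimated odds ratio across the seven cut-points of the scale, which addresses the assumption directly.

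**Working it through.** **Inputs from the documents.** Size: "We have chosen a sample size of 100 per arm for the proof of concept stages" (SAP 5). Allocation: "This process results in equal allocation of the 3 active intervention arms and the pooled placebo arm" (SAP 4.4.3), so the comparison is 1:1. Follow-up for recovery runs to Day 60, and deaths before recovery are censored at Day 60 (SAP Table 7). Control recovery (scores 1-3) at Day 8 is 0.0 + 34.6 + 1.2 = 35.8% (SAP Table 4). The remdesivir trial cited in protocol section 2.2.2 gives a median recovery time of 10 days on remdesivir and 15 on its comparator, with a rate ratio of 1.29.

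**Assumed, because the documents do not give them.** Day 60 recovery 70-90%; loss to follow-up 0-5%; control events by Day 29 of 10-25% for the low-event endpoint.

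**The plan's own figure.** The SAP states no error rate for the crossing check. Its only design figures are those of Table 5, so these were reproduced first as a check on the setup. A two-stage simulation from Table 4 (50, then 100 per arm; 40,000 replications) at OR 2 gives futility 0.028, early efficacy 0.073, and power 0.763 (alpha 0.05) and 0.910 (alpha 0.20). Table 5 has 0.028, 0.070, 0.765 and 0.913. All eight rows agree within 2 points.

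**Algebra.** Let H be the control cumulative hazard, with HR 2 up to time c and 0.5 afterwards. For t > c the treated cumulative hazard is 2H(c) + 0.5[H(t) - H(c)] = 1.5H(c) + 0.5H(t). The curves meet when this equals H(t), that is, when H(t) = 3H(c). They stay apart through Day 60 if H(60) < 3H(c). If c is the control median, H(c) = ln 2, and the condition is Day 60 recovery below 1 - exp(-3 ln 2) = 1 - 1/8 = 87.5%. A fourfold fall in HR then leaves even the true curves uncrossed.

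**Simulation.** Daily recovery times, 100 per arm, 4,000 replications per scenario (Monte Carlo SE at most sqrt(0.25/4000) = 0.8 points). A crossing means that the Kaplan-Meier difference takes both signs. The comparator is a Schoenfeld-residual test on log time at two-sided 5%. For control curves fixed at 35.8% recovery on Day 8, the percentage of trials with a crossing was:

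| True hazard ratio | Day 60 recovery 70% | 80% | 88% | Residual test rejects |
|---|---|---|---|---|
| 1.00 constant | 80 | 84 | 87 | 4-5 |
| 1.29 constant | 54 | 57 | 59 | 4-5 |
| 1.50 constant | 33 | 33 | 33 | 4-5 |
| 2.00 constant | 10 | 9 | 8 | 4 |
| 2.0 to 0.5 at Day 8 | 45 | 77 | 92 | 83-94 |
| 2.0 to 0.5 at Day 10 | 35 | 59 | 80 | 76-89 |
| 2.0 to 0.5 at Day 14 | 17 | 29 | 46 | 56-65 |
| 1.5 to 0.67 at Day 14 | 52 | 61 | 73 | 31-35 |

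With Weibull control curves (median 10 or 15 days, Day 60 recovery 70-90%) added, the ranges are:

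- HR 1: crossing in 63-87%. This is 53-79% ignoring Days 1-4, 47-74% if each arm must lead by more than 2 points at some time, and 15-32% if by more than 5 points.
- Constant HR 1.29: crossing in 30-59%. HR 1.5: 9-33%. HR 2: under 10%.
- Reversal 2.0 to 0.5 at Day 14: no crossing in 54-98%.
- The same reversal at Day 10: no crossing in 65-95% (Day 60 recovery 70%), 41-74% (80%) and 20-34% (88-90%).
- Residual test: false rejection 3.6-5.0%; detection 49-89% for the Day 10 reversal and 31-66% for Day 14.

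For a Day 29 endpoint with few events, curves cross in 70-75% at HR 1 and still in 45-50% at a constant HR of 0.5.

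**The case against.** The strongest reply is that little hangs on this check, and most of that reply stands. A reader might infer that the SAP treats a crossing as rejecting PH. It does not say so: the sentence runs in one direction only, and the next one mentions PH not being satisfied without defining it. A reader might also infer that the check decides whether the hazard ratio or RMST is used. The documents do not support that either: section 6.1 says RMST will be reported, and it is unconditional for sustained recovery and death.

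The numbers also depend on how the plots are read. Someone who ignores sign changes of 5 points or less would see far fewer chance crossings, although the SAP sets no such tolerance. At HR 1 a chance crossing does little harm, since the score test is valid there and RMST should agree.

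Nor does non-crossing pass reversals in general. A Day 8 reversal with 88% recovery crosses in 92% of trials, and an early reversal on the low-event endpoint (0.4 to Day 10, then 2.0) crosses in 83-94%.

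Finally, a residual test has only moderate power at this size. For the milder reversal in the table it rejects in 31-35%, while the curves cross in 52-73%. That comparison does not rescue the rule, because on the same control curves crossing is more frequent still (80-87%) when hazards are exactly proportional.

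**Conclusion.** The criterion is wrong as written, at low to moderate importance. It can label a fourfold change in hazard ratio as PH-supported, and it commonly withholds support when PH holds and the effect is nil or modest. The algebra needs no simulation. The percentages rest on the assumed Day 60 recovery and on counting any sign change as a crossing, so they should be read as ranges.

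The effect on the trial's conclusions is bounded. The Cox hazard ratio and score p-value remain the main time-to-event analysis whatever the curves show. The Day 8 proportional-odds analysis, the interim guidelines and the promising threshold do not use the check. What remains is a misleading diagnostic for every Cox endpoint, and a mismatch between section 6.1, which promises RMST, and the shells that omit it.

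**What to change.** 1. In SAP section 6.1, delete the parenthetical criterion.
2. Replace it with scaled Schoenfeld residuals or a treatment-by-log(time) term in each Cox model, accompanied by log(-log S) plots. State that this is descriptive, that its power at 100 per arm is moderate, and that it does not switch between analyses.
3. Add RMST differences with confidence intervals to Tables 32-33, 42-43 and 56, stating the truncation time as Table 29 does.

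The cost is about one sentence of SAP text, a few table rows and minor programming. Data collection, sample size and trial conduct do not change.
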